**Objectives:**

**Primary:** To consolidate a prospective cohort of Health Care Workers (HCWs) to generate epidemiological and clinical high quality data. This information will be relevant to improve health policies and clinical COVID-19 protocols. This cohort will also be used as an ongoing platform to implement SARS-CoV-2 research projects with particular emphasis on incidence rate, reinfection, vaccines, and long term immune response.

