To date, seroprevalence studies conducted in Spain have used cross-sectional designs. Thus, they cannot provide systematic data on long-term antibody and cellular immune responses.

Thus, thorough serological and prospective studies are needed to determine whether ADE manifests among SARS-CoV-2 infections, either because of prior homologous infection or cross-reactive antibodies from other HCoVs. This will have particular relevance for vaccination plans.

Another interesting point that deserves further analysis is analyzing the different antibody specificities generated and their dynamics. Several studies have examined various types of antibodies identified against SARS-CoV-2 (Spike1, Spike2, Nucleocapsid, envelopes), identifying variable responses [8,9]. However, little is known about the simultaneous kinetics of the different antibodies over time. This can be analyzed with our cohort and also with the antigens used in the various vaccines that will be in the market in the next months. Thus, given the virus's short evolution, it is necessary to create an exhaustively monitored cohort. This cohort will make it possible to identify the kinetics of SARS-CoV-2-specific antibodies in individuals with different degrees of severity of COVID-19 and to know which levels of antibodies are protective against new possible reinfections in 3 years.

Crucially, this serological information will be used to strategically deploy HCW immune to the infection, limiting the risk of exposure and inadvertent propagation of the virus.

In conclusion, the present study is crucial to obtain epidemiological and clinical data to improve health policies for the prevention of SARS-CoV-2 infection. In addition, the study will be conducted simultaneously with the course of the pandemic, which will make it possible to obtain real-time data on the different waves that occur and, in turn, to study the SARS-CoV-2 endemic. Therefore, ProHEPIC-19 can be used as an ongoing platform to implement SARS-CoV-2 research projects with particular emphasis on incidence rate, reinfection, vaccines, and long term immune response.

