#### 6.5. PROCEDURES

Participants entering the study after meeting exclusion/exclusion criteria (Table 1), give written informed consent (informed consent and patient information sheet, see Appendix 1) and they are assigned to a cohort (Figure 1). Cohorts are divided into:

- 1) Healthy pre-cohort: HCW exposed to but not infected with SARS-CoV-2, negative PCR-test or Ig M (N) and IgG (N)
- 2) Non-recent Infected cohort: HCW infected with SARS-CoV-2 (>15 days RT-PCR, positive)
- 3) Recent Infected cohort infected HCW : HCW with acute SARS-CoV-2 infection (<15 days RT-PCR, positive)

All participants undergo a standardised follow-up according to the specific cohort to which they are assigned (Table 2). At study entry, we record the following information: baseline socio-demographic

data, clinical data (symptoms), epidemiological data (contact with a positive and symptoms of COVID-19) (table 3), information on the work environment, data on the diagnosis of COVID-19 (previous biological samples taken and dates of sick leave due to COVID-19), use of personal protective equipment, previous health status and habits. At subsequent visits, epidemiological data, clinical data (symptoms) and vaccinations are recorded.

Finally, initial participant's cohort assignation is reviewed and reclassified on basis on laboratory results (RT-PCR test or SARS-CoV-2 antibodies IgM and IgG against the nucleocapsid (N)) in two final cohorts:

1) Health Care Workers Healthy Cohort (HCW\_H): This cohort includes HCW with negative laboratory test RT-PCR and SARS-CoV-2 antibodies IgM(N), and IgG(N).

2) Health Care Workers Infected Cohort (HCW\_I): This cohort includes HCW with positive laboratory test (RT-PCR and/or SARS-CoV-2 antibodies IgM and IgG) This cohort is subdivided into three categories according to the illness severity:

Asymptomatic or Presymptomatic Infection: Individuals with positive laboratory evidence of COVID-19 but no COVID-19 signs nor symptoms.

Mild-Moderate Illness: Individuals with positive laboratory evidence of COVID-19 who have any of the various signs and symptoms of COVID-19 (e.g., fever, cough, sore throat, malaise, headache, muscle pain, nausea, vomiting, diarrhea, loss of taste and smell) but who do not have shortness of breath, dyspnea, or abnormal chest imaging and home health care.

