#### 6.6.2. OUTCOME MEASURES

Outcome measures of immune response (SARS-CoV-2 Antibodies (N), cytokines, T-cells) and Covid-19 clinical symptoms will be measured at baseline and prospectively aiming to observe possible associations between possible prognostic factors and immune response. The baseline and prospective measurements will allow to assess their prognostic role and whether some of them appear as confounding factors.

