**Secondary Outcome Measures:**

4. Kinetics of SARS-CoV-2. IgM Nucleocapside

IgM (nucleocapside) ELISA kits (Inmunodiagnostic Limited ©). Positivity thresholds were provided by the assay manufacturers and were considered positive with an index value greater than 1.1, indeterminate from 0.9 to 1.1 and negative if <0.9 index units

[Time Frame: Baseline, 7 days, 15 days, 3, 6, 9 and 12 months after the beginning of the study]

5. Kinetics of SARS-CoV-2. IgG Nucleocapside

IgG (nucleocapside) ELISA kits (Inmunodiagnostic Limited ©). Positivity thresholds were provided by the assay manufacturers and were considered positive with an index value greater than 1.1, indeterminate from 0.9 to 1.1 and negative if <0.9 index units

[Time Frame: Baseline, 7 days, 15 days, 3, 6, 9 and 12 months after the beginning of the study]

6. Kinetics of SARS-CoV-2. IgG Spike

IgG (spike). ELISA kits DECOV1901 (Demeditec Diagnostics GmbH©). Positivity thresholds were provided by the assay manufacturers and were considered positive with an index value greater than 40, indeterminate from 32 to 40 and negative if <32 UI/ml

[Time Frame: Baseline, 7 days, 15 days, 3, 6, 9 and 12 months after the beginning of the study]

7. Kinetics of SARS-CoV-2. T-Cell

SARS-CoV-2 specific CD4+ and CD8+ T-cell responses we performed an IFN $\gamma$  ELISPOT assay. Wells will be considered positive if they contained at least 50 spot-forming cells per 10^6 PBMCs above the background level (2X mean + 3Xstandard deviation).

[Time Frame: Baseline, 7 days, 15 days, 3, 6, 9 and 12 months after the beginning of the study]

8. To assess the relation between clinical variables and initial RT-PCR results in the whole sample and by sex.

To study the differences between clinical spectrums and initial RT-PCR we will use ANOVAs or Kruskal-Wallis tests, after checking normality assumption using a Shapiro-test

[Time Frame: Baseline, to 12 months after the beginning of the study]

9. To analyse the relation between clinical variables and the interindividual differences in the immune response in early, mid, and long periods of immunization in the whole sample and by sex

To study the differences between clinical spectrums and immune response in early period we will use ANOVAs or Kruskal-Wallis tests, after checking normality assumption using a Shapiro-test . Similarly, to look for differences in antibody levels between sex, either a t-test or a Mann-Whitney test will be performed.

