##### LOCALLY ESTIMATED SCATTERPLOT SMOOTHING (LOESS) MODELS

LOESS models will fit as an initial descriptive manner of studying the antibodies, both IgM and IgG, evolution since diagnosis day. LOESS regression consists of fitting simple models (e.g., first or second degree polynomials) in subsets of data determined by a nearest neighbours algorithm. These LOESS curves will best stratified either per clinical condition or gender, and will be shown together with their 95% confidence interval (CI). We will use all the data available except for those from participants who never tested positive, grouping the data points per participant in the figures.

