##### NONLINEAR MIXED-EFFECTS (NLME) MODELS

Mixed-effects models are generally useful when there are multiple measures per participant, as in this study. Random effects are included in the model to test if they may be causing any significant, and generally unexpected, significant influence in the modelling built by the fixed effects. Therefore, introducing random effects in the model help to control unobserved variance.

We will use NLME models to study possible differences in the dynamics (kinetics) of SARS-CoV-2 antibodies (IgM, IgG) levels since symptoms onset. After fitting a general model, the differences will be studied between clinical spectrums and biological sex, setting the largest group as reference groups for modelling. To fit these models, we will use all the data available except for those from participants who never tested positive. Time after diagnosis was discretized as follows: Tests made in the first 14 days since diagnosis are treated as "Day 15". Tests from days 15 to 29, as "Day 30", days 30 to 59 as "Day 60", days 60 to 89 as "Day 90", days 90 to 179 as "Day 180", days 180 to 269 as "Day 270", days 270 to 360 as "Day 360", and days 360 up to end of follow-up as "Day 450". However, antibody values beyond 450 days after diagnosis were not considered, as they were only available for 14 participants.

The general equations to be fitted will be:

$$IgM(t) = b_1 + (b_0 - b_1)e^{-k_1 t} - b_1 k_1 (e^{-k_1 t} - e^{-k_2 t})$$

$$IgG(t) = b_1 + (b_0 - b_1)e^{-k_1 t} - b_1 k_1 (e^{-k_1 t} - e^{-k_2 t})$$

Having  $t$  normalized per the maximum number of days (360). This general equation corresponds to an equation describing an exponential rise followed by an exponential decay.  $b_0$  corresponds to the baseline value,  $b_1$  corresponds to the asymptotic value (i.e., antibody levels at  $t \rightarrow \infty$ ),  $k_1$  corresponds to the rise rate, and  $k_2$  to the decay rate.

Nonlinear mixed-effects models will be built using the nlme package [14].

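### The antibody curves keep samples taken after vaccination or reinfection, because the plan has no sample-level rule for either event

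*Combined protocol and SAP*

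**What the plan says.** Section 6.8.2.1 plans LOESS curves as a first description of the antibodies and nonlinear mixed-effects (NLME) models as the main kinetic analysis. The NLME text reads "To fit these models, we will use all the data available except for those from participants who never tested positive", and the LOESS text has the same rule: "We will use all the data available except for those from participants who never tested positive". The exclusion therefore works on whole participants. The one cut on individual samples stands in the NLME text: "antibody values beyond 450 days after diagnosis were not considered". Its stated reason is sparse data (14 participants).

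Other sections foresee both events. The objectives in the abstract place "particular emphasis on incidence rate, reinfection, vaccines, and long term immune response". The background refers to "the antigens used in the various vaccines that will be in the market in the next months". Section 6.5 states: "At subsequent visits, epidemiological data, clinical data (symptoms) and vaccinations are recorded". Section 6.7, item C, gives vaccine protection and the link between immune response and reinfection as reasons for collecting the immunological data. No section excludes, censors, flags or models samples taken after either event.

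On the antigen, section 6.6.2 opens with "Outcome measures of immune response (SARS-CoV-2 Antibodies (N), cytokines, T-cells) and Covid-19 clinical symptoms", which points to nucleocapsid (N), while secondary outcome 6 is "Kinetics of SARS-CoV-2. IgG Spike". Section 6.8.2.1 names IgM and IgG but no antigen.

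**The concern.** The NLME model is the planned analysis for the antibody half of secondary aim 1, and its comparisons by clinical spectrum and sex bear on hypotheses 1 and 2. Its late-time parameters describe how far the response to infection persists. If late samples include responses to a second exposure, those parameters no longer describe the first infection alone. The model then has nowhere to put the second rise except its fitted parameters, random effects or residuals. In the LOESS curves such samples are simply pooled with the rest.

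A secondary point is that both analyses select on ever having tested positive, but section 6.8.2.1 does not say which of the plan's positivity criteria it means. Workers positive on serology alone can enter the curves as infected, so the data set is partly selected on the outcome being modelled.

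**Working it through.** The plan states no figure on this point, so there is none to reproduce. Its sample-size calculation (section 6.4) is for a two-group ANOVA and does not bear on the curves.

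**1. Can the equation show a second rise?** Section 6.8.2.1 gives, for both isotypes,

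y(t) = b1 + (b0 − b1)e^(−k1·t) − b1·k1·(e^(−k1·t) − e^(−k2·t)).

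Its derivative is

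y′(t) = −k1(b0 − b1 − b1·k1)e^(−k1·t) − k1·k2·b1·e^(−k2·t).

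Setting it to zero gives e^((k2 − k1)t) = b1·k2/(b1 + b1·k1 − b0). When k1 and k2 differ, this holds for at most one t. The curve has at most one turning point, so it cannot rise, fall and rise again.

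**2. Does the 450-day cut remove later exposures?** It runs from diagnosis, not from any vaccination date. By section 6.3 the study starts on 31 March 2020 and recruitment is expected to end on 15 June 2021. Day 450 is 24 June 2021 for a worker diagnosed on the first date and 8 September 2022 for one diagnosed on the second. The cut does not separate samples before and after vaccination.

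**3. How large could the effect be?** The documents give no vaccination coverage and no antibody levels, so v and r below are assumptions. Let a share v of late samples be post-vaccination, at r times the unvaccinated mean m. The crude late mean is (1 − v)m + v·r·m = m[1 + v(r − 1)], so the multiplier is:

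| | v = 10% | v = 25% | v = 50% |
|---|---|---|---|
| r = 1 | 1.00 | 1.00 | 1.00 |
| r = 2 | 1.10 | 1.25 | 1.50 |
| r = 5 | 1.40 | 2.00 | 3.00 |

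These are factors for a crude mean, not for b1 or k2. The effect on b1 and k2 would depend on the true curve, parameter bounds and starting values.

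**4. What happens to group comparisons?** The ratio of late means is off by [1 + vB(r − 1)]/[1 + vA(r − 1)].

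- vA = vB, same r: 1, no distortion.
- vA = 25%, vB = 50%: 1.50/1.25 = 1.20 (r = 2); 3.00/2.00 = 1.50 (r = 5).
- vA = 10%, vB = 50%: 1.50/1.10 = 1.36 (r = 2); 3.00/1.40 = 2.14 (r = 5).

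**5. Which positivity criterion applies?** The wordings differ:

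- Abstract: RT-PCR and/or antibodies, with the antibodies tied to baseline.
- Section 6.5, final infected cohort: RT-PCR and/or antibodies, with the two isotypes joined by *and*.
- Section 6.6, item 8 (symptom onset) and item 16 B (who gets Spike testing): RT-PCR or either N isotype.

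Item 16 B gives the N cut-offs as positive above 1.1 and indeterminate from 0.9 to 1.1. Section 6.8.2.1 refers to none of these and does not say how indeterminate results count.

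The N assays' stated specificity is 93.3%, so the false-positive rate is 1 − 0.933 = 6.7% per test, if that figure applies to a single assay. Section 6.6.2 lists seven antibody time points. Over seven tests, the chance that a never-infected worker is ever positive on one assay runs from 6.7% (errors fully correlated) to 1 − 0.933^7 = 38.5% (errors independent). Fewer tests lower the upper end.

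**The case against.** The vaccine part is conditional. Section 6.6.2 labels the antibody outcome N, and section 6.8.2.1 writes paired IgM and IgG equations. Among the secondary outcomes only N has both isotypes; Spike has IgG alone. The curves can therefore be read as N only, and the documents do not say that the vaccines raise N antibodies. This stands as a condition. It does not remove the point, because on that reading secondary outcome 6 has no kinetic analysis anywhere in the plan, and reinfection could still affect N.

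A reader might infer that the comparisons by spectrum and sex are biased. Step 4 shows that this needs a different vaccination share or response between the groups, and nothing in the documents says that either differs.

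A reader might also infer that testing positive is undefined. That goes too far: cut-offs and criteria exist, and the Spike-testing rule in section 6.6, item 16 B, is the closest match to the wording of the curves. What is missing is a cross-reference, with the handling of indeterminate results and timing. Differences in how the final cohorts are worded do not matter here, because the curves are not selected by cohort.

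Finally, the 93.3% is one figure given for IgM and IgG together and may be a combined value. The range in step 5 is therefore illustrative.

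**Conclusion.** The point holds, with moderate confidence, and should be fixed. Followed as written, the plan keeps post-vaccination and post-reinfection samples in curves that are meant to describe the response to infection, and the NLME equation cannot represent a second rise. If Spike IgG is modelled, and assuming vaccination raises it, its long-term level (b1) and decay rate (k2) would mix the two responses. Reinfection could do the same to any marker.

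The size cannot be computed from the documents. The multipliers of 1.0 to 3.0 for a crude late mean, and of 1 to 2.14 for a ratio between groups, rest wholly on the assumed v and r. No size is given for the reinfection part. The primary aim is not affected. The positivity question is a smaller, separate gap.

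**What to change.** - **Antigen.** Reconcile the opening of section 6.6.2 with secondary outcome 6, and name the antigen for each curve in section 6.8.2.1.
- **Vaccination.** In the main fits, censor Spike IgG at the first recorded vaccination and report later samples separately, or keep them with a time-varying vaccination term. For N, either state the assumption that the vaccines used do not raise it, or censor it in the same way as a sensitivity analysis.
- **Reinfection.** Define a documented reinfection and censor all antibody markers there. Section 6.6, item 16 A, plans RT-PCR every 2 weeks, and section 6.7, item B, lists RT-PCR results in the health records; name the source to be used.
- **Data.** Add vaccination date to the variable lists in sections 6.6 and 12, which omit it although section 6.5 records vaccinations. Check that the dates are complete.
- **Positivity.** Cross-reference one criterion in section 6.8.2.1, covering indeterminate results and whether a positive at any visit counts. Add a sensitivity analysis of the kinetics and the clinical-spectrum comparisons in RT-PCR-confirmed participants, which does not select on the antibody outcome.

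Write these rules before the fits. The past tense of the 450-day sentence suggests that some follow-up data had already been seen, so state what was known when each rule was set.

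The cost is SAP wording, one definition and a check of the vaccination records. The price in data is fewer late samples and wider late intervals. Workers vaccinated before their first positive test would give no Spike samples to the main fit. The RT-PCR-confirmed set will be smaller, possibly with few asymptomatic participants.

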**Secondary:**

1. To determine the kinetics of SARS-CoV-2 antibodies and cellular immune response in early, mid, and long periods of immunization.
2. To assess the relation between clinical variables and initial RT-PCR results with the interindividual differences in the immune response in early, mid, and long periods of immunization.
3. To analyze differentially expressed cytokines as biomarkers of disease progression in early, mid, and long periods of immunization.

**Methods and analysis:** Longitudinal, dynamic, prospective cohort study with a 12-month follow-up, which is being conducted in 4 primary-care centres and one hospital of Northern Metropolitana Nord of Barcelona (Spain). For now, the study consists of 1350 participants divided into 2 cohorts: 1) Healthy-Exposed HCWs: 675 not infected by SARS-CoV-2 (RT-PCR with a negative result and negative SARS-CoV-2 antibodies at baseline) and 2) Infected HCWs: 675 symptomatic participants (those with new persistent cough, temperature  $\geq 37.5^{\circ}\text{C}$ , anosmia, or ageusia or other compatible symptoms with COVID-19) or asymptomatic participants diagnosed by positive RT-PCR test and/or SARS-CoV-2 antibodies (IgM, IgG at baseline). Primary outcomes include: humoral and cellular immune response, quantitative antibodies to SARS-CoV-2, SARS-CoV-2 antibody levels related to progression phenotype, clinical spectrum of SARS-CoV-2, symptomatology, demographics and other variables that may be predictive of immune response.

**Follow-up:** baseline, 15 days, 1, 3, 6, 9 and 12 months.

**Findings to date:** Current literature has shown that the immune response is maintained for a minimum of 2 months. Nevertheless little is known about the association between the immune response and the progression phenotype of COVID-19.

**Future plans:** This prospective cohort offers the possibility to study associations between immune response and progression phenotype according to age and gender as well as long-term immune response. In turn, we will be able to examine possible cumulative effects, taking into account several

clinical variables. The study is ongoing and we plan to extend it to increase the size of the cohort until 2024.

**Ethics and dissemination:** The study is approved by the Ethics Committee (IDIAPJGol ref 20/067-PCV IGTP ref COV20/00660 (PI-20-205). Dissemination will occur through presentations at National and International conferences and publications in international peer-reviewed journals.

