**TABLE 5. Protocol to be followed according to the cohort of inclusion in the study**

[figure not shown]
Visit	Study Cohorts	Protocol
0	All possible participants	Telephone screening/personal interview to explain the study and to decide if is an eligible participant and pre-cohort
1	Healthy Health Care Workers (HCW)	RT-PCR (SARS-CoV2) Anti-SARS-CoV-2 IgG and IgM antibodies Hemogram and serum biochemistry
	Infected HCW	RT-PCR (SARS-CoV2) Anti-SARS-CoV-2 IgG and IgM antibodies Hemogram and serum biochemistry T-cells (INF $\gamma$ Elispot assays, Combinatorial flow-cytometry) Citokines multiplex assay
	Healthy HCW	No visit
2	Infected HCW	Telephone symptoms control call
3	Healthy HCW	No visit
	Infected HCW with positive RT-PCR in Visit 1 or previously	With positive RT-PCR in Visit 1 or previously: RT-PCR (SARS-CoV2) and Anti-SARS-CoV-2 IgG and IgM antibodies

		with negative RT-PCR in visit 1 and previously: Anti-SARS-CoV-2 IgG and IgM antibodies
	Healthy HCW	No visit
4	Healthy HCW	Anti-SARS-CoV-2 IgG and IgM antibodies
	Infected HCW	Anti-SARS-CoV-2 IgG and IgM antibodies T-cells (INF $\gamma$ Elispot assays, Combinatorial flow-cytometry) Citokines multiplex assay
	Healthy HCW	RT-PCR (SARS-CoV2) Anti-SARS-CoV-2 IgG and IgM antibodies Hemogram and serum biochemistry
5	Healthy HCW	with antibodies in Visit 4: Anti-SARS-CoV-2 IgG and IgM antibodies, T-cells (INF $\gamma$ Elispot assays, Combinatorial flow-cytometry) Citokines multiplex assay
		without antibodies in Visit 4: Anti-SARS-CoV-2 IgG and IgM antibodies
	Infected HCW with positive RT-PCR in Visit 1 or previously	Anti-SARS-CoV-2 IgG and IgM antibodies, T-cells (INF $\gamma$ Elispot assays, Combinatorial flow-cytometry) Citokines multiplex assay

	Infected HCW with negative RT-PCR in visit 1 and previously	with antibodies in Visit 4: Anti-SARS-CoV-2 IgG and IgM antibodies, T-cells (INF $\gamma$ Elispot assays, Combinatorial flow-cytometry) Citokines multiplex assay
		without antibodies in Visit 4: Anti-SARS-CoV-2 IgG and IgM antibodies
	Healthy HCW	with antibodies in Visit 4: Anti-SARS-CoV-2 IgG and IgM antibodies, T-cells (INF $\gamma$ Elispot assays, Combinatorial flow-cytometry) Citokines multiplex assay
		without antibodies in Visit 4: Anti-SARS-CoV-2 IgG and IgM antibodies
6	Healthy HCW	with antibodies in Visit 4: Anti-SARS-CoV-2 IgG and IgM antibodies, T-cells (INF $\gamma$ Elispot assays, Combinatorial flow-cytometry) Citokines multiplex assay

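### Workers without a positive RT-PCR enter the antibody curves only through an N index above the cut-off, so part of the kinetic sample is selected on the modelled outcome and no analysis by entry route is planned

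*Combined protocol and SAP*

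**What the plan says.** Section 6.8.2.1 sets one inclusion rule for both kinetic analyses. For LOESS: "We will use all the data available except for those from participants who never tested positive". For the mixed-effects models: "To fit these models, we will use all the data available except for those from participants who never tested positive". Neither paragraph defines a positive test.

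The definition has to come from elsewhere:

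- The abstract describes infected participants as "diagnosed by positive RT-PCR test and/or SARS-CoV-2 antibodies (IgM, IgG at baseline").
- Section 6.5 reviews cohort assignment on "RT-PCR test or SARS-CoV-2 antibodies IgM and IgG against the nucleocapsid (N"), and defines the infected cohort thus: "This cohort includes HCW with positive laboratory test (RT-PCR and/or SARS-CoV-2 antibodies IgM and IgG").
- Section 6.6, in item 8 and in the laboratory assays, accepts N IgM or N IgG as confirmation. Spike IgG is measured only in workers already positive by RT-PCR or N serology, so it is not a further way in.
- Table 5 has follow-up rows for "Infected HCW with negative RT-PCR in visit 1 and previously".

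The modelled outcomes are N IgM and N IgG, read as "considered positive with an index value greater than 1.1, indeterminate from 0.9 to 1.1 and negative if <0.9 index units" (section 6.6.2, outcomes 4 and 5). Section 6.8.2.1 then compares the curves between clinical spectrums and sexes.

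**The concern.** The kinetic sample has two entry routes with different selection. An RT-PCR-positive worker is in, even if every antibody result is negative. A worker without a positive RT-PCR is in only after crossing the cut-off on the assay being modelled. An infected worker who was RT-PCR-negative or untested and whose N index never passed 1.1 contributes nothing to the curves and meets the healthy-cohort definition in 6.5. Random effects cannot correct for this, because such workers supply no data to the fit.

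Hypothesis 1 is that kinetics differ by clinical spectrum, and secondary aim 1 concerns response over early, mid and long periods. A fixed cut-off removes more of a low-responding class than of a high-responding one. Section 4 reports the highest responses in the more severe spectrum. The selection would therefore tend to raise the milder classes and narrow the contrast. No RT-PCR-confirmed fit, adjustment for entry route or sensitivity analysis is described.

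**Working it through.** **Plan's own figure.** The 522 per group in 6.4 reproduces: noncentral F, two groups, η² = 0.01, alpha 0.05, power 0.9005 at n = 522; 522/0.90 = 580. It concerns a comparison of two cohort means and does not bear on this point. The plan gives no figure for the curves.

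**Inputs.** From the documents: cut-off 1.1, sensitivity 92.5%, specificity 93.3%, 675 per cohort. Assumed, because the documents are silent: the serology-only share q of an analysed class, the proportion p of infections above the cut-off, and the antibody distributions.

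**Step 1: shift in one class.** For a normal log level, entry above the cut-off raises the mean of the serology-only part by φ(z)/p SD, with z = Φ⁻¹(1 − p). The class mean rises by q·φ(z)/p.

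| p | φ(z)/p | q = 10% | q = 25% | q = 50% |
|---|---|---|---|---|
| 0.925 (stated sensitivity read as p) | 0.153 | 0.02 | 0.04 | 0.08 |
| 0.80 | 0.350 | 0.04 | 0.09 | 0.17 |
| 0.60 | 0.644 | 0.06 | 0.16 | 0.32 |

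**Step 2: ratio between two classes.** Assume true geometric mean N indices of 1.5 (asymptomatic) and 2.5 (mild-moderate), ratio 0.60, and log10 SD 0.25 to 0.45.

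Worked case: SD 0.35, half of asymptomatic infections confirmed by RT-PCR, all mild-moderate confirmed.

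- z = (log10 1.1 − log10 1.5)/0.35 = (0.0414 − 0.1761)/0.35 = −0.385, so p = 0.650.
- The mean above the cut-off is 0.3756.
- The asymptomatic mean is (0.5 × 0.1761 + 0.325 × 0.3756)/0.825 = 0.2547, where 0.325 = 0.5 × 0.650.
- The observed ratio is 10^(0.2547 − 0.3979) = 0.72.

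The same formula over the SD range gives:

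| RT-PCR-confirmed share of infections | Observed ratio (true 0.60) |
|---|---|
| asymptomatic 50%, mild-moderate 100% | 0.67–0.77 |
| asymptomatic 50%, mild-moderate 75% | 0.66–0.71 |
| 50% in both | 0.65 |
| asymptomatic 50% with p set to 0.925, mild-moderate 100% | 0.63–0.65 |

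For the last row, the serology-only share is 0.4625/0.9625 = 0.481. At SD 0.25 the shift is 0.25 × 0.153 × 0.481 = 0.0184 and 0.60 × 10^0.0184 = 0.63. At SD 0.45 the shift is 0.0331 and the ratio is 0.65.

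**Step 3: severe minus asymptomatic, in SD.** Take severe p = 0.95 and q = 5%, which adds 0.005 to the severe mean.

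- Asymptomatic p = 0.80, true gap 0.80: observed 0.72 at q = 25% and 0.63 at q = 50%.
- Asymptomatic p = 0.60, true gap 1.39: observed 1.24 at q = 25% and 1.07 at q = 50%.

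The attenuation is about 10% to 23%. It does not need unequal shares: with q = 25% in both classes, the second gap is 1.39 + 0.03 − 0.16 = 1.26.

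**Step 4: opposing force.** A single test round in 675 uninfected workers gives 675 × (1 − 0.933) = about 45 false positives. These enter under the same rule. They probably lie near the cut-off and turn negative on retest, which lowers levels and apparent persistence.

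**The case against.** The strongest reply is that the serology-only group may be small. Section 6.5 defines both infected pre-cohorts by a positive RT-PCR, section 6.6 describes RT-PCR every two weeks, and section 4 says that workers with symptoms or high-risk contacts await RT-PCR. Part of this stands: the share is unknown, and if it is small the shift is a few hundredths of an SD. But Tables 2 and 5 do not schedule two-weekly RT-PCR, such testing could not find infections cleared before enrolment, and the final classification in 6.5 adds serology.

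It could also be said that a positive test in 6.8.2.1 means RT-PCR only. Sections 2, 6.5 and 6.6 do not support that reading.

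RT-PCR-confirmed cases are themselves selected on access to testing. Restricting to them changes the population from the protocol's infected cohort and does not recover infected workers who never tested positive. This stands, and argues for two analyses side by side.

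A reader might infer three stronger things that the documents do not support:

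- *The gradient reverses.* Under the assumptions of Step 2, the ratio exceeds 1 (1.14) only if every asymptomatic worker is found by serology, the mild-moderate class has no truncation and the SD is 0.45. With both classes found entirely by serology it is 0.73 to 0.78.
- *Serology-only workers are mostly asymptomatic.* This is plausible, but no passage gives the share by severity. In Table 2 the rows with negative RT-PCR sit within the recent-infected pre-cohort, which receives symptom calls.
- *Durability is overstated by a known amount.* A calculation that admits workers on their first test alone does not match the plan, which excludes only those never positive over repeated visits on either marker. No persistence figure is given here for that reason. False positives also pull the other way.

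**Conclusion.** The concern holds in a limited form. On the documents' own definitions, the serology-only part of the kinetic sample is selected on the modelled outcome, the RT-PCR-positive part is not, and nothing in the plan separates them.

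The likely effect is an attenuated clinical-spectrum gradient, with levels and persistence overstated in serology-only entrants. This depends on low responders being commoner in milder disease. Under the assumed values a true ratio of 0.60 appears as about 0.63 to 0.77 with mixed entry. The effect is negligible if few enter by serology alone or nearly all infections exceed the cut-off. The net direction is not certain: false positives can offset part of it, entry through IgM does not directly select on IgG (or the reverse), and spike IgG is affected only through its correlation with N.

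This should be fixed, but it does not threaten the primary aim: the kinetics are secondary outcomes, and the primary aim is to build and describe the cohort.

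**What to change.** In section 6.8.2.1:

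1. State that a positive test means RT-PCR and/or N serology. Settle whether serology requires IgM and IgG (the wording in 6.5) or either one (the wording in 6.6).
2. Pre-specify the LOESS and mixed-effects curves and the clinical-spectrum contrast in RT-PCR-positive participants, keeping all their antibody results including negatives, beside the all-positive analysis.
3. Show serology-only entrants as a separate stratum, by clinical spectrum, with the sample that qualified them left out of the fit. Report their number.
4. Base conclusions on severity and durability on agreement between the two analyses, or on the RT-PCR-confirmed fit if they differ.

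RT-PCR results are already recorded (section 6.7), so the change needs SAP wording and one stratifying variable. The cost is wider intervals, especially in the asymptomatic class. The report should also say that RT-PCR-confirmed cases depend on who was tested.
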